
	
both drugs in 10.7%, interruption of either drug in 69.9%, and dose reduction of axitinib in 20.3% of the patients in 1st line RCC of any risk (Rini TI et al, 2019). During the treatment with avelumab + axitinib 42% of the patients had at least one reduction in the dose of axitinib due to AEs and in 8% of the patients AEs led to a discontinuation of both avelumab and axitinib (Motzer R et al, 2019). Based on this, an important objective of this study is to gain more insights how widespread the existing national guidelines are followed for the 1L treatments in this patient population. Additional objectives are to describe the frequencies of dose modifications and temporary/permanent discontinuations as well as the proportions of modifications by dose reductions in connection with drug combination of ICI + TKI and ICI + ICI in the standard care setting of urologists and hematologists in practices and hospitals in Germany.

Research questions and objectives	
 • How is the effectiveness, defined as measurement of beneficial effects under “real world” clinical settings, (e.g. progression-free survival, overall survival and best response) of TKI and/or ICI as 1L in patients with aRCC? • How are patients with aRCC treated in 1L under daily care conditions in Germany in general and in accordance to medical specialities (urology and medical oncology) and treatment settings (hospitals vs office-based practices)? • Are all patients assigned to individual risk ratings under standard daily care conditions according to a scale developed by the IMDC before start of a 1L? • How are patients treated in 1L in different risk rating groups and how is the adherence to national/international guidelines? • What kind of previous and subsequent therapies are administered before and after 1L? • How often are evaluations for PD-L1 expression performed before start of 1L and how many patients are positive (TPS $\geq 1\%$) or negative? • How long are patients treated with TKI + ICI and ICI + ICI in 1L in general and in relation to specific therapies like avelumab + axitinib? • How frequent are dose modifications and early discontinuations and what are the reasons?

- Are there differences in the handling of modifications among medical disciplines?

To answer these questions the following objectives are derived:

Primary Objective(s):

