Population	
Inclusion criteria for part 1 and 2:
 
 • Patients aged ≥ 18 years old • Patients with histologically/cytologically confirmed renal cell carcinoma (International Classification of Disease 10.revision (ICD)-10 C64) • Full medical information regarding all treatments before, during and after 1L should be available. 
Specific inclusion criteria only for Part 1:
 
 • Patients with locally advanced or metastatic disease and a start of any systemic 1L therapy against RCC between 01 January 2020 and 31 December 2021 
Specific inclusion criteria only for Part 2:
 
 • Patients with locally advanced or metastatic disease, who were treated with a combination of ICI + TKI or ICI + ICI as 1st line therapy against RCC and who had a completion of this therapy between 01 January 2020 - 31 December 2021 with a follow-up period of at least 3 months after completion of the 1L. 
Exclusion criteria for part 1 and 2:
 
 • Patients participating in an interventional clinical study within 30 days before start of 1L.
Outcomes	
The following clinical outcomes are of relevance in the study and should be answered regarding the research questions:
 
Primary Outcome
 
 ○ Progression-free survival in 1L in median and at defined timepoints after start 
Secondary outcomes

	
○ Overall survival rates from start of 1L therapy, expressed as median and at pre-defined timepoints○ Proportions of different therapy protocols used in 1L○ Best responses to 1L therapies○ Duration of response to 1L therapies○ Time-to-progression to 1L therapies○ Time-to-next-therapy to 1L therapies○ Frequency of modifications and discontinuations in 1L○ Reasons for modifications and discontinuations in 1L○ Treatment continuation after modifications and discontinuations in 1L (for all therapies and in relation to specific protocols like axitinib + avelumab or nivolumab + ipilimumab) 
Other Outcomes
 
○ Distribution of 1L therapy by age, gender and risk rating○ Distribution of 1L therapy and frequency of modifications/discontinuations by medical speciality and institution

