	
assumed for part 2, that also the number of patients with combination therapies in part 2 (n = 300) will grant a representative statement to all research questions. Based on information of urological and oncological experts as well as own data of the GermanOncology ^{*1} network (see below), the following assumptions could be set:
 
• Number of patients with new 1L in urological practices (per practice 1- 3 urologists) = 4 - 6 per year
○ Number of patients with new 1L in period of 24 months = 8 - 12• Number of patients with new 1L in oncological practices (per practice 2- 4 oncologists) = 4 - 6 per year
○ Number of patients with new 1L in period of 24 months = 8 - 12• Number of patients with new 1L in hospitals with urological focus = 8 - 12 per year
○ Number of patients with new 1L in period of 24 months = 16 - 24• Proportion of 1L therapies in urological and oncological practices: 50% : 50%• Proportion of patients treated with 1L in practices and hospitals (as most of therapies are oral therapies): 65% : 35% 
Based on the assumptions the needed number of sites are at least:
 
• Number of urological practices: 15• Number of oncological practices: 15• Number of hospitals with urological focus: 10• Total number of sites across Germany: 40 
<small>^{*1} GermanOncology operates a permanent network of 25 oncological practices across Germany, is collecting longitudinal RWE data about several tumor entities since 2012 and is able to analyze data from more than 25.000 patients with around 25 different tumor entities</small>

Data Analysis	
The following clinical outcomes will be measured:
 
Primary outcome:
 
○ PFS in 1L:
▪ described as median and rates of patients without disease progression or death for any cause at defined timepoints (6, 9, 12 and 18 months) after start of 1L therapy. 
Secondary outcomes:
 
○ OS in 1L

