	
 ▪ Defined as median and rates of patients alive at pre-defined timepoints (12 and 18 months) after start of 1L therapy. ○ Proportion of different drug regimen in 1L 
 ▪ Defined as percentages of therapy protocols used as 1L therapy. ○ Best response rate (RR) in 1L 
 ▪ Defined as best response (complete response (CR) / partial response (PR) / stable disease (SD) / progressive disease (PD) / not done (ND)) recorded from the start of the therapy until disease progression/recurrence based on investigator's assessment. A confirmation of response is not required. ○ Duration of Response (DoR) in 1L 
 ▪ Defined as time from documentation of first disease response to disease progression. ○ Time to progression (TTP) in 1L 
 ▪ Defined as time from start of therapy until objective disease progression without including deaths. ○ Time to next treatment (TTNT) in 1L 
 ▪ Defined as time from last drug administered to initiation of next therapy. ○ Dose modifications and discontinuations in 1L 
 ▪ Defined of number of patients with at least 1 dose modification (reduction of dose or cancelling of administration) or with an interim/permanent discontinuation of one or all drugs of a therapy. ○ Handling after dose modification or discontinuations in 1L 
 ▪ Defined as continuation of therapies after dose modifications or temporary/permanent discontinuation of single drugs. 
The clinical outcomes will be analyzed for the total group of all patients and for following subgroups:
 
 ○ Age: < 70 years vs. ≥70 years ○ Gender: male vs. female ○ Risk rating: favorable (low) vs. intermediate vs poor (high) risk ○ Medical disciplines: urology vs. medical oncology ○ Institutions: practices vs. hospitals
Milestones	
Planned milestones:
 
 ● Start of data collection: 1 October 2022 ● Interim analysis (expected): 31 October 2022 ● End of data collection: 30 January 2023 ● Final study report: 15 April 2023

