In pivotal studies, a higher rate of modifications and discontinuations of one or both drugs were seen for combinations of ICI (pembrolizumab or avelumab) + axitinib. During the therapy with pembrolizumab + axitinib AEs of any cause led to discontinuation of either drug in 30.5%, discontinuation of both drugs in 10.7%, interruption of either drug in 69.9%, and dose reduction of axitinib in 20.3% of the patients in 1L line RCC of any risk ([Bini TI et al, 2019](#)). During the treatment with avelumab + axitinib 42% of the patients had at least one reduction in the dose of axitinib due to AEs and in 8% of the patients AEs led to a discontinuation of both avelumab and axitinib ([Motzer R et al, 2019](#)). In the pembrolizumab-plus-lenvatinib group, AEs of any grade led to discontinuation of lenvatinib, pembrolizumab, or both drugs in 37.2% of patients (lenvatinib, 25.6%; pembrolizumab, 28.7%; both drugs, 13.4%), to dose reduction of lenvatinib in 68.8% of patients and to interruption of lenvatinib, pembrolizumab, or both drugs in 78.4% of patients ([Motzer R et al, 2021](#)). A comparable situation could be found for combination of Nivolumab + Ipilimumab as also for this combination dose delays were described in up to 58% and discontinuations in up to 22% ([Motzer R et al, 2018](#)).

But the present handling of severe AEs in the standard care setting of combinations ICI + TKI or ICI + ICI in 1L RCC (e.g. dose reduction or interim discontinuation of axitinib or interim/permanent discontinuation of both drugs) seems to be unclear as no detailed data are available.

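### Modification and discontinuation frequency is split by discipline and by institution but never within regimen, so a different regimen mix can look like different handling

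*Combined protocol and SAP*

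**What the plan says.** The research questions in the Abstract and in section 8.1 include this one: "Are there differences in the handling of modifications among medical disciplines". Section 7 gives particular weight to how intolerability of combination therapy is handled, and to differences between urologists and medical oncologists and between practices and hospitals.

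Three parts of the Abstract bear on the analysis:

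- Under Outcomes, the plan lists "Distribution of 1L therapy and frequency of modifications/discontinuations by medical speciality and institution".
- Under Data Analysis, the measure is "Defined of number of patients with at least 1 dose modification". A dose reduction or a cancelled administration counts as a modification, and an interim or permanent discontinuation of one or all drugs also counts.
- The same row says: "The clinical outcomes will be analyzed for the total group of all patients and for following subgroups". The list is age, gender, risk rating, discipline ("Medical disciplines: urology vs. medical oncology") and institution. Regimen is not on it.

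Regimen-specific reporting is stated for best response, PFS and duration of response (section 8.2) and for continuation after a modification (Abstract, Outcomes). None of it is crossed with discipline or institution.

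Part 1 admits any systemic first-line therapy, while Part 2 admits combinations only (section 9.1.1). Section 9.1.2 announces Part 2 quotas by regimen group but states none per discipline or institution. Section 9.6 leaves detailed methods to a SAP whose content is not in the supplied text.

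**The concern.** For regimen to distort the contrast, it must affect the outcome and its mix must differ between the groups.

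The protocol documents the first condition. For avelumab + axitinib, "42% of the patients had at least one reduction in the dose of axitinib due to AEs". With pembrolizumab + axitinib the axitinib reduction figure is 20.3%. For pembrolizumab + lenvatinib, section 8 reports that adverse events led "to dose reduction of lenvatinib in 68.8% of patients".

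The second condition is open. Section 7 makes differing therapeutic behaviour between disciplines and settings a study question, so equal mixes cannot be assumed, and nothing in the design balances regimen across the groups.

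If the mixes do differ, the pooled split combines which regimen a discipline prescribes with what it does when that regimen is poorly tolerated. A discipline that uses more of a regimen with frequent reductions would appear to modify more, even if its practice within each regimen were identical. Section 7 hopes the results will help unify processes and develop standard recommendations, so the two need to be separable.

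**Working it through.** **The plan's own figure.** No size or precision is stated for this comparison. The only sized quantity is the PFS rate in section 9.4. With z = 1.96, π = 0.5, E = 0.05 and N = 10,000, the formula gives 9,604 / (0.9604 + 24.9975) = 369.98, which rounds up to the stated 370. It does not bear on this point.

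**Inputs** (pivotal-study rates as cited in section 8; some also appear in the Abstract):

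| Regimen | TKI dose reduction | Interruption or delay | Discontinuation of any drug |
|---|---|---|---|
| Pembrolizumab + lenvatinib | 68.8% | 78.4% | 37.2% |
| Avelumab + axitinib | 42% | not given | not given |
| Pembrolizumab + axitinib | 20.3% | 69.9% | 30.5% |
| Nivolumab + ipilimumab | not given | up to 58% (delays) | up to 22% |

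**Method.** Give both groups the same rate within each regimen, so that handling is identical. The crude rate in a group is the sum of (regimen share × regimen rate), and any crude difference is then artefact. The mixes are assumptions.

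**Step 1: dose reduction alone, three regimens.** Shares are in the order pembrolizumab + lenvatinib / avelumab + axitinib / pembrolizumab + axitinib.

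- 60/20/20: 0.6 × 68.8 + 0.2 × 42 + 0.2 × 20.3 = 53.7%
- 20/20/60: 0.2 × 68.8 + 0.2 × 42 + 0.6 × 20.3 = 34.3%
- Difference: 19.4 points

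The middle share is equal in both groups and cancels, so this is 0.4 × (68.8 − 20.3). For 50/25/25 versus 25/25/50 it is 0.25 × 48.5 = 12.1 points. For 40/30/30 versus 30/30/40 it is 0.10 × 48.5 = 4.9 points.

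**Step 2: nearer to the defined outcome.** The plan's measure also counts cancelled administrations and discontinuations. If interruptions count, the cited interruption rates are floors for the composite. Using them as stand-ins, the gap is 78.4 − 69.9 = 8.5 points, and the same three mixes give:

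- 0.4 × 8.5 = 3.4 points
- 0.25 × 8.5 = 2.1 points
- 0.10 × 8.5 = 0.9 points

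With a floor of 69.9% for pembrolizumab + axitinib, the composite for pembrolizumab + lenvatinib can exceed it by at most 100 − 69.9 = 30.1 points. The artefact in that direction is then at most 0.4 × 30.1 = 12.0 points for this pair at the widest mix.

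**Step 3: other pairs, two regimens, mirror-image mixes.** The artefact is (2s − 1) × gap, where s is the larger share.

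| Pair and component | Gap | 60:40 | 70:30 | 80:20 |
|---|---|---|---|---|
| Pembrolizumab + lenvatinib vs nivolumab + ipilimumab, interruption vs delay | 20.4 | 4.1 | 8.2 | 12.2 |
| Avelumab + axitinib vs pembrolizumab + axitinib, dose reduction | 21.7 | 4.3 | 8.7 | 13.0 |
| Pembrolizumab + lenvatinib vs nivolumab + ipilimumab, discontinuation | 15.2 | 3.0 | 6.1 | 9.1 |

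The nivolumab + ipilimumab rates are upper figures and are not defined in the same way as the others.

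**Step 4: precision once regimen is held constant.** The artefact is then zero by construction. Assume that the 300 Part 2 patients split 150 versus 150 over two regimens with rates of 42% and 20.3%. At 70:30 the strata are 105 vs 45 and 45 vs 105, so the Mantel-Haenszel weights are equal. The variance is 0.25 × (0.42 × 0.58 + 0.203 × 0.797) × (1/105 + 1/45) = 0.00322, and the 95% half-width is 1.96 × √0.00322 = 11.1 points. At 60:40 it is 10.4 points, and at 80:20 it is 12.7 points.

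**The case against.** The strongest objection concerns size. Dose reduction is one component of a broad composite, and on the only pair with interruption rates from the same kind of count the artefact falls to between about 1 and 3 points. That is well below the 10 to 13 point half-width of a stratified estimate. This stands: a reader might infer that the planned pooled frequency could be off by some 19 points, and the documents do not support that for the outcome as defined.

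Two further inferences also fail:

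- The study-size line "Proportion of patients treated with 1L in practices and hospitals (as most of therapies are oral therapies): 65% : 35" per cent might be read as evidence that regimen mix differs by setting. It only explains why most patients are treated in practices, and says nothing about discipline.
- A two-drug regimen has more chances to score than TKI monotherapy, but this applies only to Part 1, since Part 2 excludes monotherapy.

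It can also be said that continuation after modification is a separate outcome with some reporting by protocol, that the regimen distribution will appear beside the frequency, that the Abstract's rationale names regimen class and care setting together, that the contrast is descriptive, and that the SAP may add detail. All of this is true. But continuation is not crossed with discipline or institution either, and separate marginal tables show a difference in mix without removing it. The combinations themselves differ in their rates, so limiting Part 2 to them, with quotas not set per discipline, does not remove the problem.

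**Conclusion.** The point holds as a modest, inexpensive improvement. The protocol asks whether handling differs between disciplines, and the stated analysis cannot separate that from a difference in regimen mix, in Part 1 or among the combinations in Part 2.

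The size is uncertain and depends on the component. At the widest assumed mix it is about 19 points for dose reduction alone and about 3 points with interruption rates standing in for the composite. For pembrolizumab + lenvatinib against nivolumab + ipilimumab it is about 4 to 12 points on interruption versus delay, with rates that are not defined identically.

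All these figures assume identical handling within regimen, pivotal-study rates carried over to routine care, and regimen mixes that the documents do not give. With equal mixes the artefact is zero. The documents do not show that the mixes will differ; they leave it as a question to be answered.

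**What to change.** In the Outcomes and Data Analysis rows of the Abstract, or in the SAP:

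1. Report frequency separately for dose reduction, cancelled administration and discontinuation, together with continuation afterwards. Do this by discipline and by institution within regimen class: ICI + TKI, ICI + ICI and, in Part 1, TKI monotherapy.
2. Where numbers allow, repeat this within avelumab + axitinib and nivolumab + ipilimumab.
3. Add one summary difference per contrast with a 95% CI, either standardised to the pooled regimen mix or from a model with regimen as a factor.
4. Label the pooled split as descriptive only.

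No new data are needed, since regimen, discipline and location are already captured (section 9.2). The cost is extra tables, smaller cells and wider intervals; the half-width of about 10 to 13 points at an assumed 150 versus 150 should be stated alongside the results.

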8.2. Study Objectives

To answer these questions the following objectives are derived:

Primary Objective(s):

- Progression-free survival (PFS) for 1L therapies, expressed as median and as rates at timepoints of 6, 9, 12 and 18 months after start of 1L

Secondary Objectives:

- Overall survival (OS) of 1L therapies, expressed as median and rates at timepoints of 12 and 18 months after start of 1L therapy
- Best response in 1L overall and in dependence of administered drug regimen
- Progression-free survival of 1L therapies in dependence of specific drug regimen
- Pre- and post-treatments (i.e. surgery, radiotherapy, medicinal therapies) before/after TKI + ICI and ICI + ICI in 1L
- Duration of response (DoR) in 1L overall and in dependence of administered drug regimen (TKI + ICI or ICI + ICI)
- Frequency of dose modifications and temporary/permanent discontinuations of 1L therapies and their reasons
- Proportions of modifications by dose reduction compared to cancelling single applications
- Effectiveness (PFS, OS and best response) of administered 1L therapies under real world conditions by medical specialty (urology, medical oncology) and setting (practice, hospital)

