Supportive drugs prescribed during 1L	Relevant for outcomes	Medical Chart	Administered supportive drugs in connection with cancer therapy
Date of first response and best response in 1L incl. date and mode of assessment	Relevant for outcomes	Medical Chart	dd/mm/yyyy; CT/MRI/ultrasound/x-ray; clinical assessment; laboratory
Assessment of first and best response in 1L	Relevant for outcomes	Medical Chart	CR/PR/SD/PD/ND
Date of tumor progression	Relevant for outcomes	Medical Chart	dd/mm/yyyy
Reasons for end of 1L	Relevant for outcomes	Medical Chart	Progression; intolerance; decision oncologist; patient's wish; death; deterioration performance
Subsequent therapies (Second-line therapy (2L) and higher) with drugs/protocol and dates for start / end	Relevant for outcomes	Medical Chart	y/n; used drugs/regime; start/stop
Concomitant diseases and therapeutic measures	Relevant for outcomes	Medical Chart	Detailed diagnosis; therapeutic measures OP/medicinal/none/other

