9.6. Data analysis

The data analysis are carried out for all evaluable patients for whom the inclusion criteria are met, first-line therapy with at least 1 application has been documented and no exclusion criteria exist.

Detailed methodology for summary and statistical analyses of data collected in this study will be documented in a statistical analysis plan (SAP), which will be dated, filed and maintained by the sponsor. The SAP may modify the plans outlined in the protocol; any major modifications of primary endpoint definitions or their analyses would be reflected in a protocol amendment.

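### Duration of response has no end event for death without progression, and its start is not tied to CR or PR, so the onset date can be lost for some responders

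*Combined protocol and SAP*

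**What the plan says.** Section 4 (Data Analysis) gives the only definition of DoR: "Defined as time from documentation of first disease response to disease progression". It does not mention death or censoring. Two neighbouring outcomes in the same list do address death. PFS is "described as median and rates of patients without disease progression or death for any cause at defined timepoints", and time to progression is "Defined as time from start of therapy until objective disease progression without including deaths".

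Best response in that list takes CR, PR, SD, PD or not done (ND), is assessed by the investigator, and "A confirmation of response is not required". No section says that response, for DoR, means CR or PR.

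Table 2 (Section 9.2) has two response rows. One is "Date of first response and best response in 1L incl. date and mode of assessment". The other is "Assessment of first and best response in 1L", with CR/PR/SD/PD/ND as its permitted values. Table 2 has no separate date of first CR or PR and no date of death; death appears only as a reason for the end of first-line therapy.

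Section 8.2 lists DoR as a secondary objective, overall and by regimen. On the analysis population, Section 9.6 states: "The data analysis are carried out for all evaluable patients for whom the inclusion criteria are met". It sets no responder subset for DoR and leaves detailed methods to a SAP, of which no separate text is in the supplied document. Section 9.3 says that, because of full anonymisation, data management cannot send queries.

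**The concern.** There is a weakness at each end of the interval.

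- **End.** A responder who dies without documented progression has no DoR event. If that patient is censored at death, the estimate describes time to progression among responders, and the reported duration is longer than the time patients remained alive and in response. Such deaths may include deaths from toxicity, and handling of intolerability is a stated focus of the study.
- **Start.** Because SD and PD are permitted values of first response, one site may enter the first tumour assessment of any kind and another the first CR or PR. DoR would then depend on how each of about 40 sites reads the item. Patients who never responded could be given a duration, and some true responders could have no recorded date of response onset.

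A later SAP can settle the population and the end event. It cannot supply a date that was not collected and cannot be queried.

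**Working it through.** **The plan's own figure.** The documents give no number for DoR. The one calculation they do give, the sample size in Section 9.4, reproduces. With z = 1.96, π = 0.5, E = 0.05 and N = 10,000, z²π(1−π) = 0.9604, so n = 0.9604 × 10,000 / (0.9604 + 0.0025 × 9,999) = 369.98, rounded up to 370. DoR does not enter this formula, so 370 and the planned 400 are not affected.

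**End event.** The inputs are assumptions: constant hazards, a progression-only median of 15 months, and a hazard h of death without progression of 0.005 or 0.01 per month.

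- Progression hazard: ln 2 / 15 = 0.0462 per month.
- Median time to progression or death: ln 2 / (0.0462 + h).
- h = 0.005: 0.6931 / 0.0512 = 13.5 months; deaths are 0.005 / 0.0512 = 9.8% of end events.
- h = 0.01: 0.6931 / 0.0562 = 12.3 months; deaths are 0.01 / 0.0562 = 17.8% of end events.

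Censoring deaths would report 15 months, which is 1.5 or 2.7 months too long under these inputs. Put the other way, if the progression-or-death median is m and a share d of end events are deaths, censoring them gives m / (1 − d). For m = 15 and d from 5% to 30%, this is 15.8 to 21.4 months. If patients who die unprogressed were dropped rather than censored, these figures would not apply.

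**Who could enter.** Section 8 quotes objective response rates of 51.4% to 71% for ICI + TKI. Applied to the 300 patients of Part 2, this gives 300 × 0.514 = 154 to 300 × 0.71 = 213 responders, leaving 146 to 87 others. These are upper bounds on the non-responders who could enter. They assume that the ICI + TKI rate holds for all of Part 2 and that every non-responder has a dated first assessment.

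To see the direction of the effect, assume a responder median of 15 months, a median of 6 to 9 months from a first SD to progression, and 10% to 20% of patients with PD at first assessment (duration 0). The pooled median solves ORR × 2^(−t/15) + SD share × 2^(−t/s) = 0.5, where s is the SD median and the SD share is 1 − ORR − PD share. It lies between 7.0 months (ORR 51.4%, PD 20%, s = 6) and 11.3 months (ORR 71%, PD 10%, s = 9), against 15 for responders alone. This error therefore runs opposite to the omission of deaths.

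**Onset date.** Take a hypothetical patient with SD at month 3, PR at month 6, CR at month 12 and PD at month 20.

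| Start used | DoR (months) |
|---|---|
| SD, entered as first response | 20 − 3 = 17 |
| PR, actual onset | 20 − 6 = 14 |
| CR, best response | 20 − 12 = 8 |

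If the site enters SD as first response, month 6 is in neither date field. If the site reads first response as first CR or PR, month 6 is recorded. If the course is SD then PR with no CR, the best-response date can serve as onset, provided it is the first date of PR.

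**The case against.** The strongest reply is that disease response is most naturally read as CR or PR, since the plan spells out SD and PD as stable and progressive disease. On that reading the date in the example is captured and DoR is 14 months. The five-value list may simply be shared between first and best response in one table row, and the eCRF itself is not among the documents. The category is recorded beside the date, so an analyst can drop patients whose best response is not CR or PR without changing the form. On deaths, the plan uses a progression-only outcome deliberately in time to progression, and the SAP may refine the protocol.

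Much of this stands. A reader might infer that every SD-only patient will receive a DoR; the documents do not say so, and the recorded category allows exclusion. A reader might also infer that onset dates are generally lost. The loss is confined to SD (or ND), then PR, then CR, at sites that enter the earlier assessment as first response, and the documents do not show how many patients follow that course.

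The reply does not remove the rest. Progression is the only written end event, nothing ties response to CR or PR, and a SAP cannot restore an uncollected date. For time to progression the exclusion of deaths is stated; for DoR there is no such statement and no censoring rule.

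**Conclusion.** The point holds as a defect in a secondary outcome that should be corrected. As written, DoR does not count death without progression, and it is overstated if those deaths are censored. The start is open to a reading that admits non-responders, which is avoidable at analysis, and that loses the onset date for one response sequence, which is not.

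The size is unknown. It would be tempting to say that the plan overstates DoR by 1.5 to 2.7 months, but that range follows from an assumed median and assumed death hazards, none of which is in the documents. The two errors act in opposite directions, so the net bias cannot be signed. Nor do the documents support a claim that a regimen comparison is invalidated: DoR is reported overall and by regimen, and no formal test of it is described. The PFS definition and the sample size of 370, or 400 with buffer, are untouched.

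**What to change.** Before data collection (planned start 1 October 2022):

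1. In Table 2 and the eCRF, replace the first-response item with the date and mode of first CR or PR, left empty if neither occurred. Keep best response as CR/PR/SD/PD/ND.
2. Define DoR only in patients with a best response of CR or PR, from first CR or PR to progression or death from any cause, whichever comes first. Censor patients without an event at the last documented assessment.
3. Confirm that the eCRF captures date of death, or add it. Section 9.5 says documentation runs up to the present date, death or loss to follow-up, so the date may be there, but Table 2 does not list it. PFS and OS need it too.

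The cost is one relabelled item, possibly one added date field, and a revised definition. Fewer patients will enter the DoR analysis than if non-responders were admitted, and the reported duration will be somewhat shorter where responders die without progression.
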